Methods: This is a single arm study to assess the effectiveness of an experimental telehealth intervention within the treatment of ESLD, and compare it with a historic cohort. All inpatients with advanced liver disease and at least 1 complication will be eligible to participate. The study group receives the Telehealth intervention and will be given an ipad/smartphone preloaded with the instruments used for symptom monitoring and cognitive function assessment during the hospital admission. A research coordinator will consent the patients and conduct a 30-minute introduction to use of device on the day of enrollment (within 24-48 hours of admission). The second assessment will be done on day 2, and third assessment on day of discharge. After that, the patient will be told to do the study assessments daily at home. The study assessment results will be reviewed by the providers on the same day, and based on the severity scores clinical actions will be taken and documented.

IV. Expected Research Outcomes and Benefits -
--

Primary Outcomes:

- 1) Healthcare utilization (30 and 90-day readmission)
- 2) Changes in severity scores of symptoms and quality of life over time.

3) Patient experience/satisfaction.

Benefits of the research: Applying telehealth intervention (inclusive of remote monitoring of symptoms and cognitive function) with a well-defined clinical algorithm at the time of discharge of patients with ESLD, who are prone to impaired quality of life, adds a **new dimension** to the care delivery model. This new post-hospital discharge algorithm is expected to have positive effects on many parameters, including readmission rates, patient satisfaction, and above all on the health outcomes. Arguably, these improvements will reduce health care costs among a group of patients with ESLD, who are high utilizers of healthcare services. Benefits to individual patients include monitoring of their own symptoms, and cognitive function, which will allow early detection of hepatic encephalopathy and/or other complications.

VII. Evaluation Component and Research Evaluative Procedures - Oversight and Statistical Tests

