Oversight: The PI will be overseeing the implementation of the project along with the Co-Investigator. Since the study involves patients who are admitted to the hospital, and offers them a device to improve their own care, the likelihood of participation is high. We will assess the attrition rates and other technical issues during the project. Higher rates of no response to timed assessments from enrolled patients will trigger an alert to the research coordinator, who will then call the patients to make sure device is working appropriately and explore the reasons for missing responses. Furthermore, a detailed discussion at the time of enrollment about the project and expected responsibilities from patients will reduce the missing data points.

Statistical Tests: The data for study group will be described using both graphic and summary statistics. Process data on participation, usage and satisfaction with telehealth intervention will be collected and summarized to assess intervention fidelity. We will assess the change in percent readmissions at 30 days and 90 days in the study group from baseline to 3 months. The average rate of change in the defined outcomes in longitudinal (overtime) analyses using paired t tests and 95% CIs of the differences in the two groups will be conducted. The trajectories of symptom and quality of life scores will be illustrated by graphing individual patient values over time course of the study for the intervention group. We will test whether the relationship between study outcome and study arm differ with the severity of disease as assessed by MELD (Model for End Stage Liver Disease) score using two-way analysis of variance for repeated measures.

(B) Performance Measures

B) Performance measures:

- 1) Number of patients enrolled in the study.
- 2) Completion of 7, 28 days and 3 months assessment of symptoms and cognitive function by the patients.

- 3) Attrition rates of enrolled patients.
- 4) Efficiency of the technical device provided to patients as assessed from ease of use by patients and providers.
- 5) Scholarly activities (publications and presentations) resulting from study data.

VIII. Health Disparities

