“HGE healthcare solutions” is a group of experts who have pioneered some work in telehealth, and created a smartphone based COPD app (Chronic Obstructive Pulmonary Disease), which assesses daily symptoms and triggers alerts to providers for immediate treatments. This app has shown to improve health outcomes and reduce hospitalizations by changing the approach of health care to proactive than reactive. ^{v vi} We will be partnering with this company in creating and delivering our telehealth intervention. The company operates on a HIPAA secured platform, which maintains confidentiality and security of the data. They also offer technical assistance to end users during normal business hours.

(3) Research Design, Methods and Activities -
--

Methods: This is a single arm trial to assess the effectiveness of an experimental telehealth intervention within the treatment of ESLD, and compare it with a historic control. The study patients continue to receive the routine standard of care, which may involve addressing symptoms based on individual needs and circumstances. All participants will be given an ipad/smartphone preloaded with the instruments used for symptom monitoring and cognitive function assessment. A research coordinator will consent the patients and conduct a 30-minute introduction to use of device on the day of enrollment. Repeat assessments will be done as shown in **Table 1** above. All patients will receive the standard of care discharge planning, including discharge instructions and a confirmed follow-up ambulatory visit within 2-4 weeks.

Inclusion Criteria: All patients being discharged from the inpatient liver practice of the Einstein Healthcare Network (EHN) who meet the following criteria will be eligible.

- ✓ Patients must be age 18 years or older
- ✓ Ability to provide informed consent, and must be able to cognitively answer questionnaires
- ✓ Patients who received a diagnosis of Advanced Liver Disease with at least 1 of the complications (Hepatorenal Syndrome, Portal Hypertension, Ascites, Hepatic Encephalopathy)
- ✓ Patient must be able to read/ speak English
- ✓ Patient must have a support person

Exclusion Criteria:

- ✓ Cognitive impairment which precludes participation
- ✓ Projected survival, in the opinion of the provider, of less than six months
- ✓ Current psychosis or confusion, precluding a patient from being consented
- ✓ Patients being discharged to nursing homes

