- ✓ Patients with red green color blindness (as they will not be able to respond to stroop test questions).

Telehealth Intervention:

Patients will receive a 30-minute introduction to the use of ipad/smartphone, and instructions to respond to the following assessments. Initial assessments will be performed on the day of enrollment, and all of them will be repeated periodically (**Table 1**), for a total of 3 months study

participation. The assessments include the following: Pain (severity, location), shortness of breath (at rest or with mild activity), cognitive function assessment (drowsy, hard time concentrating, irritable, trouble remembering things, slurred speech, unsteady gait), and stroop test (color matching test, one cycle lasts 45 seconds).

Weight monitoring: Monitoring weight will allow assessment of fluid retention in ESLD patients, and help detect any development/ worsening of ascites. Patients will be instructed to enter their daily weights for the first month, and then every week for next 2 months. Any weight gain of more than 2 lbs within 1-2 days for 3 consecutive days will trigger a phone call by the providers.

A simplified step by step guide summarizing the instructions will be included with the device. Patients will be given a toll-free number that will be available during work hours (9am to 5pm) for any technical issues, and will be urged to complete assessments by 11 am on a daily basis.

Site: Levy 7 is the home of the “Liver Care Center at Einstein”, a 15 bed inpatient unit dedicated to the care of patients with liver disease. This inpatient unit is the site of identification and recruitment of patients in this project.

Recruitment methods: The research coordinator will contact eligible patients within 24-48 hours of admission and conduct informed consent. All patients who consent will be then randomized to either of the 2 groups. We assume 3-4 patients will be enrolled per week, for 7 months of enrollment period.

Sample size and power: Assuming a baseline risk of readmission in the historic control of 40% and 10% attrition rates, a sample size of 50 patients will be sufficient to detect a difference of 35% or greater in the intervention group. Accepting a type I error rate of no more than .05, and a Type II error rate of .20, we will have 80% statistical power to detect a difference of this magnitude or larger.

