Retention strategies: Patients will be informed about the purpose of the study and their responsibilities at the time of consent by the research coordinator. All patients with a support person will be eligible. Strategies (i.e. education about value of study participation) will be added if recruitment rates fall within 20% of target.

Analysis plan: Medical records will be utilized to capture the disease severity, diagnosis, duration of liver disease and presence of comorbidities. Patients enrolled into the study will be followed up for 6 months. Descriptive and analytics statistics will be done using linear correlation and regression. We will compare the clinical markers at baseline with 3 month value using unpaired t test.. .

Limitations:

Patient Attrition: this is an anticipated problem, as physical and cognitive deterioration may make the completion of questionnaires difficult. This limitation will be minimized by the short interval assessments and completion of study at 3 months.

(4) Protection of Human Subjects -

- (a) **Risks to subjects:** There is no medical risk to any participant and no sharing of protected health information in this project. It is completely up to the participants to agree for this study. Refusal for participation will not impact their health care in the office. There are minimal risks to participants related to their completion of survey questionnaires. There may be some emotional distress as they complete the symptom and quality of life questions, but this will influence and enhance their own care. Patients may have technical difficulties, which will be addressed through availability of a help desk and the research coordinator during work hours.
- (b) **Adequacy of protection against risks:** There are no known risks in this study. All study personnel have completed the IRB required CITI training, and will be trained appropriately. Confidentiality is maintained through Einstein's secured system and the secure administration through HGE. The PI and Co-Investigator will be available to answer any of the patient's concerns. The research coordinator will conduct an in-depth informed consent explaining the purpose of the project, and the expectations from patients to respond to the assessments in a timely way. All the information collected is through a secured password protected system, which allows encrypted data transmission to the providers

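### Under the single-arm design, the planned MELD-by-study-arm repeated-measures ANOVA cannot be carried out for any listed primary outcome; it looks like a remnant of a two-arm plan

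*Combined protocol and SAP*

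**What the plan says.** Section VII, Statistical Tests, states: "We will test whether the relationship between study outcome and study arm differ with the severity of disease as assessed by MELD". The method given is "using two-way analysis of variance for repeated measures". The sentence does not say which outcome is meant, how MELD is grouped or coded, or which time points enter.

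The design is described twice as single-arm. Section II (Methods) says "This is a single arm study to assess the effectiveness of an experimental telehealth intervention". Section XI(3) says "This is a single arm trial to assess the effectiveness of an experimental telehealth intervention", and that the study will "compare it with a historic control". In XI(3) every participant receives the device.

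Recruitment methods, also in XI(3), says the opposite: "All patients who consent will be then randomized to either of the 2 groups".

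On severity data, the Analysis plan says "Medical records will be utilized to capture the disease severity, diagnosis, duration of liver disease and presence of comorbidities", without saying whether this covers the historic patients. The Data Safety Monitoring Plan schedules chart-based laboratory values at baseline, 4 weeks and 3 months, for this study. The only figure given for the historic group is an assumed 40% readmission risk (Sample size and power).

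**The concern.** A test of whether severity modifies the effect of study arm needs both arms to supply the outcome and the modifier. A historic group cannot have answered an app that this project sets out to build, so for app scores there is no second arm. For readmission a second group may exist, but the stated model does not suit the outcome.

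If the sentence stays, the analyst must choose the outcome, the model and the MELD grouping after the data are in. A second issue is related. Study and historic patients are not randomized against each other, so a difference in severity could bias the readmission comparison in Aim 2. MELD is a natural adjustment variable, but the plan does not say whether it will be used that way.

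**Working it through.** **Step 1. What the test requires.** (i) At least two arm levels; (ii) a repeated quantitative outcome observed in each; (iii) MELD in each, grouped if it is an ANOVA factor. No cut-off is given.

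**Step 2. The candidate outcomes against those requirements.**

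| Outcome | Repeated and quantitative? | Available in historic group? |
|---|---|---|
| App symptom and cognitive scores | Yes | No: the tool is developed under Aim 1 and given to participants |
| Quality of life | Change over time is planned | No historic collection described |
| Device satisfaction | Not described as such | No: those patients had no device |
| Readmission, 30 and 90 days | No: two yes/no flags, and a readmission by day 30 is also one by day 90 | Possibly; only an assumed 40% risk is given |
| Chart laboratory markers (not a listed primary outcome) | Yes | Possible in principle; collection described for this study only |

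Section VII also plans score trajectories for the intervention group alone.

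**Step 3. Degrees of freedom for app scores.** With *a* arms and *k* MELD groups, the interaction has (a − 1)(k − 1) degrees of freedom. With a = 1 this is 0 × (k − 1) = 0 for every *k*.

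**Step 4. Which design the sample size implies.** Section XI(3) gives N = 50, control risk 40%, difference 35%, attrition 10%, type I error 0.05 and power 80%. Sidedness, and whether 35% is absolute or relative, are not stated. Reading it as two equal groups, two-sided, 40% against 5%, with mean risk 0.225:

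n per group = [1.96·√(2·0.225·0.775) + 0.8416·√(0.40·0.60 + 0.05·0.95)]² / 0.35² = (1.157 + 0.451)² / 0.1225 ≈ 21.1, so 22.

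Total 44; 44/0.9 = 48.9, so 49. Per group, 22/0.9 = 24.4, so 25, which makes 50. The stated figure is reproduced. A one-sided test with continuity correction gives the same result.

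Other readings do not reproduce it (two-sided):
- One sample against a fixed 40%, to 5%: 11 patients, 13 after attrition.
- One sample, 35% relative (40% to 26%): 91 patients, 102 after attrition.
- Two groups, 35% relative: 176 per group; 352/0.9 = 391.1, so 392 in total.

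So N = 50 fits two concurrent groups of 25, which agrees with the randomization sentence and the study-arm wording in Section VII.

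**Step 5. What a readmission interaction could show.** The plan gives no figure for this, so these inputs are assumptions: 45 evaluable study patients (50 × 0.9), MELD split 50:50, historic risk 40% in both halves, study risk 12% in one half and 40% in the other (an extreme modification), two-sided 0.05. The difference in differences is 0.28. With *h* historic patients:

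Variance = (0.12·0.88 + 0.40·0.60)/22.5 + 2·(0.40·0.60)/(h/2); power ≈ Φ(0.28/SE − 1.96).

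| h | SE | Power |
|---|---|---|
| 45 | 0.192 | 31% |
| 90 | 0.161 | 41% |
| 135 | 0.150 | 46% |
| 450 | 0.132 | 56% |

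More historic patients help only slowly, because the 45 study patients set a floor on the variance.

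**The case against.** The strongest reply is that the design itself is in doubt. If patients really are randomized to two groups, a concurrent arm exists and the empty-arm argument may fall away. That stands as a reason to settle the design first. It does not rescue the sentence as the text now reads, because two sections say single arm and every participant receives the device. The documents do not support inferring that a randomized comparison will take place, nor does the match of N = 50 to two groups prove it.

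Some stronger readings are tempting and should not be drawn:

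- *Only app scores and readmission could enter the test.* Section VII does not limit the outcome, and chart markers are a third kind that could be repeated in both groups. They are not listed primary outcomes, so the point holds for those that are.
- *Quality of life is collected on the device.* The visible text does not say so; the device is described for symptoms and cognition, and the assessment schedule (Table 1) is not visible. What can be said is that no historic collection is described.
- *MELD adjustment is ruled out.* The Analysis plan mentions regression without naming covariates, next to capture of disease severity. Adjustment is unspecified, not excluded.
- *Historic charts are already in use, so adding MELD is cheap.* No section says this; the 40% may be only a fixed rate.

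That historic patients lack app scores is itself an inference, but a firm one.

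**Conclusion.** The point holds for the analysis as written: under the single-arm design, no listed primary outcome is a repeated quantitative measure available in both groups. For app scores the interaction has zero degrees of freedom; for readmission the model is wrong and historic MELD is not described.

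A reader might infer that the effect-modification question can have no valid answer at all. The documents do not support that. For readmission it could be addressed with a suitable model if patient-level historic data exist. The answer would be non-randomized and weak: about 31% to 56% power with 45 to 450 historic patients, under the extreme assumptions in Step 5.

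The severity is should-fix. Effect modification by MELD is not among the specific aims, the primary outcomes or the inputs to the sample size. The conclusion rests on the single-arm statements governing and on historic patients not having used the tool.

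**What to change.** 1. **Reconcile the design text first.** Bring Sections II, VII and XI(3) into agreement, including the randomization sentence and the sample-size basis. If two concurrent groups are intended, rewrite the MELD test for that design and state which assessments the control group completes.

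2. **If single-arm is confirmed, replace the MELD sentence for the scores.** Within the study cohort, fit a linear mixed model with time, baseline MELD as a continuous variable, and MELD x time. Interpret MELD x time only as an association between severity and trajectory, not as modification of a treatment effect.

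3. **For readmission, make the model conditional.** State whether patient-level readmission and MELD can be obtained for the historic cohort. If so, fit a logistic regression with cohort, continuous index-admission MELD and cohort x MELD for a stated window. Define MELD by one rule in both cohorts, for example from the first laboratory values within 48 hours of the index admission. Label the interaction exploratory and low-powered, and report the MELD-adjusted cohort effect. If those data are not available, drop the arm-by-MELD test.

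**Cost.** Items 1 and 2 are mainly changes of text. Item 3 adds chart extraction; if no patient-level historic cohort yet exists, assembling one is a larger task. Historic patients without a complete MELD drop out of that model, and their number should be reported.

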This project will target the patient population at Einstein, which is largely underserved, and minority. No racial/ethnic or gender group will be excluded from the proposed study. Furthermore as the study involves providing an ipad/smartphone to patients, it eliminates any existing disparity of access for anyone who participates.

XI. Research Plan

(1) Specific Aims

The **specific aims** are:

1. To develop and implement a systematic clinical approach for remote monitoring of symptoms and cognitive function in ESLD patients, through assembling specific apps on an ipad/smartphone using web based cloud technology (referred to as telehealth intervention).
2. To evaluate the impact of our telehealth intervention on health care utilization (30/90 day readmissions)
3. To assess prospectively the comparative efficacy of telehealth intervention within the treatment of ESLD, in improving i) symptom scores, ii) patient reported quality of life, and iii) satisfaction with device and questionnaire. We hypothesize that Telehealth intervention will show improvement in these domains over time [a 10% improvement in scores from baseline to 3 months will be considered clinically significant]

(2) Background and Significance

End-Stage Liver Disease (**ESLD**) is one of the ten leading causes of death in US.ⁱ Hospitalization rates due to ESLD and its complications have skyrocketed by 93% (due to *hepatorenal syndrome*), 62% (due to *portal hypertension*), and 190% due to Hepatitis C and its complications from 2004-05 to 2010-11.ⁱⁱ Developing interventions which can potentially reduce readmissions and healthcare utilization are a national priority according to the Affordable Care Act.ⁱⁱⁱ **Telehealth** offers a unique platform to remotely monitor individual patients and offer enhanced care at the time of need, and has shown success in congestive heart failure, lung disease and diabetes.^{iv} There is no research demonstrating its utilization or efficacy for liver disease patients. Hence, we propose to develop and test the effectiveness of a ***T-Liver intervention*** to remotely monitor the symptoms (pain, shortness of breath) weight, temperature, and cognitive function (using symptom questions and a stroop test) to reduce healthcare utilization, improve patient satisfaction and health outcomes.

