- (c) **Recruitment of subjects:** All patients discharged from the Inpatient liver unit who meet the eligibility criteria will be approached for consent. Once the patients agree to participate, the details of the study and device operations will be discussed. If the patient needs more time to decide, we will allow them to take the information home and get back to the research coordinator within 1-2 days.
- (d) **Informed consent:** An in-depth informed consent will be conducted in person using paper version. The IRB approval will be attached.
- (e) **Data confidentiality** and provision of medical or professional intervention, if needed: Einstein Healthcare Network's Human Research Protection Program (HRPP) is a comprehensive system to ensure the protection of the rights and welfare of subjects in Human Research. It is comprised of the EHN leadership, Office of Research and Technology Development (ORTD), Institutional Review Board (IRB), investigators and their study staff and relevant departments and units. The HRPP not only promotes compliance with relevant laws, regulations and professional and ethical standards at all levels, it addresses the needs and concerns of researchers and enhances support of their endeavors. The HGE has a secured system through which the patients will

complete the study assessments and communicate with providers. All data collected will be completely confidential, and will not be shared with anyone outside of this project.

- (f) **Potential benefits** of the research to subjects: Since this study involves close monitoring of symptoms and development of any hepatic encephalopathy, it will enhance patient centered care through timely management of symptoms, and early detection of complications of ESLD.
- (g) **Importance of knowledge to be gained:** The knowledge gained from this project will enable the use of technology in care of liver disease patients in a meaningful way, and allow early detection of symptoms/ problems which will trigger clinical actions as needed and thereby make the approach to care more proactive than reactive. This will potentially engage patients in their own care, and improve the healthcare service delivery model for ESLD.
- (h) Inclusion of women, children and minorities in the research: All eligible candidates more than 18 years of age are included in this study, irrespective of any specific race / sex, etc.

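### Aim 3 claims comparative efficacy, but its only criterion is a 10% before-after change in the treated cohort, which recovery from the index admission could meet without any telehealth effect

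*Combined protocol and SAP*

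**What the plan says.** Aim 3 in Section XI (1) is "To assess prospectively the comparative efficacy of telehealth intervention within the treatment of ESLD", applied to symptom scores, patient-reported quality of life and satisfaction. The hypothesis attached to it is improvement over time, and "a 10% improvement in scores from baseline to 3 months will be considered clinically significant". Section IV lists change in symptom severity and quality of life among the primary outcomes.

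The Methods paragraphs in Sections II and XI (3) describe a single-arm study to be compared with a historic cohort. Section VII (Statistical Tests) plans paired t tests, confidence intervals for differences between two groups, and graphs of individual trajectories. The only number given for the historic control is the 40% readmission risk in Sample size and power.

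On timing, Section II places the introduction to the device "on the day of enrollment (within 24-48 hours of admission"), and then: "The second assessment will be done on day 2, and third assessment on day of discharge". Section XI (3), Telehealth Intervention, says: "Initial assessments will be performed on the day of enrollment, and all of them will be repeated periodically", referring to Table 1. It adds: "The assessments include the following: Pain (severity, location), shortness of breath (at rest or with mild activity), cognitive function assessment", followed by the Stroop test.

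Other passages place recruitment nearer discharge. The Inclusion Criteria in XI (3) refer to patients who are being discharged. Section XI (4)(c) says: "All patients discharged from the Inpatient liver unit who meet the eligibility criteria will be approached for consent". For those who need longer to decide, "we will allow them to take the information home and get back to the research coordinator within 1-2 days".

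**The concern.** Comparative efficacy needs scores from patients who did not have the intervention. The plan describes such data for readmission only. For scores, what remains is each patient's change from baseline to 3 months.

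That change starts at an unfavourable moment. Section I describes the disease as one of acute exacerbations with severe symptoms, and the first scores are taken during such an admission. Standard care, which may itself address symptoms (XI (3), Methods), continues throughout. Recovery, standard care and regression to the mean all act on the same contrast as the device. Deterioration, which the Limitations paragraph anticipates, acts the other way.

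At stake is a primary outcome. A 10% change labelled clinically significant under an aim of comparative efficacy would be read as a benefit of telehealth, although the contrast cannot separate the device from the course of the illness.

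**Working it through.** **The plan's own figures.** The 10% criterion has no derivation to reproduce. The sample size of 50 can be reproduced as a two-arm total: 40% against 5%, two-sided 0.05, 80% power, no continuity correction gives 22 per arm, and 44/0.9 = 48.9, or 49 after attrition. It concerns readmission and lends no support to the score criterion.

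**Inputs from the documents.** Sample size 50 with 10% attrition, so n = 45; the 10% threshold.

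**Assumptions, none given in the documents.** The 10% applies to the group mean. Lower scores are better. The 3-month mean is set to 1. The SD is CV = 0.3, 0.4 or 0.5 of that mean. The correlation between the two scores is ρ = 0.3, 0.5 or 0.7. The baseline mean is raised by d SDs, to 1 + d·CV. The telehealth effect is zero.

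**Formula.** The criterion is met when the 3-month mean is at most 0.9 times the baseline mean. With normal means,

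P = Φ{ [0.9(1 + d·CV) − 1] / [(CV/√n)·√(1.81 − 1.8ρ)] },

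where 1.81 = 1 + 0.9² and 1.8 = 2 × 0.9.

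**Worked cell** (CV 0.4, ρ 0.5, n 45). The standard error is (0.4/6.708) × √0.91 = 0.0569.
- d = 0: numerator 0.9 − 1 = −0.100; z = −1.76; P = 0.04.
- d = 0.3: numerator 0.9 × 1.12 − 1 = 0.008; z = 0.14; P = 0.56.

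**Range over the nine combinations of CV and ρ:**

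| Baseline elevation | Chance of a mean fall of 10% or more, no telehealth effect |
|---|---|
| none | 0.1-12% |
| 0.2 SD | 8-45% |
| 0.3 SD | 28-74% |
| 0.5 SD | 76-99% |

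The expected fall equals 10% when d·CV = 1/0.9 − 1 = 0.111, that is d = 0.37, 0.28 or 0.22 for the three CVs.

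**Sensitivity to the assumptions.**
- Larger SDs: with CV 0.8-1.2, the range is 13-31% with no elevation and 81-95% at 0.3 SD.
- Deterioration: with scores 0.3 SD lower at baseline than at 3 months, the chance of an apparent 10% improvement is below 1%.
- Later enrolment: if 20% or 40% of patients enrol late with no elevation, 0.3 SD becomes 0.24 or 0.18 SD on average, and the range is 14-56% or 6-41%.
- Discharge-day start: if half of a 0.3 SD elevation has resolved by discharge (0.15 SD left), the range is 4-35%. If half of a 0.5 SD elevation has resolved (0.25 SD left), it is 16-59%.

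**The case against.** The strongest reply is that a comparator is planned. Both Methods paragraphs announce a historic comparison without limiting it to readmission, and Section VII speaks of differences between two groups. A reader might infer from the aim's criterion that there is no comparator at all; the documents do not support that. What stands is narrower: no source of historic symptom, quality-of-life or satisfaction scores is described.

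Second, the aim says only baseline. Enrolment day is the natural reading, but it is an inference. Table 1 is not in the available text, so it would be wrong to say that baseline is undefined, or that enrolment to 3 months is the stated criterion. The discharge-time recruitment wording could also shift some or all first scores later, which would weaken the recovery argument. The passages conflict and need reconciling.

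Third, aim 3 hypothesises improvement over time, and a threshold of clinical significance marks relevance, not cause. That is fair, but the aim's own wording calls the result comparative efficacy.

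Fourth, the planned trajectory graphs could reveal an early inpatient fall. They could, but no passage ties them to the 10% criterion.

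Fifth, the SDs and the group-mean reading are assumed, so the percentages show direction and not a bound. That stands in full.

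A reader might also take the sentence on randomisation under Recruitment methods as supplying concurrent controls. It contradicts the single-arm design, must be reconciled separately, and adds no weight here.

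**Conclusion.** The concern holds in this form: as described, the score data can show within-cohort change but not comparative efficacy. If baseline is the enrolment-day score, recovery and standard care could meet the 10% criterion with no telehealth effect, and deterioration could hide a real one. The size is unknown; the illustrative ranges depend on the assumed elevation, SD and correlation, and on applying 10% to the group mean.

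Three stronger readings are not supported. The documents do not show that recovery would meet the criterion, because they give no score means, SDs or recovery size, and excluding confused patients may make the elevation smaller. They do not time quality of life in the available text, so for that score only the comparative wording is challenged. They do not list the Stroop test under aim 3, so the 10% criterion should not be assumed to cover it.

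The sponsor should correct this: a primary outcome is affected and the correction is cheap. Confidence is medium.

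**What to change.** 1. Name a source of historic scores on the same instruments. If there is none, replace *comparative efficacy* in aim 3 with *within-cohort change* for symptom and quality-of-life scores, describe satisfaction as a descriptive outcome after use of the device, and do not present a 10% change as a telehealth effect.
2. For the aim 3 symptom scores (pain, breathlessness, and the cognitive symptom questions if they count as symptoms; not Stroop unless the sponsor includes it), state that baseline is the enrolment-day score, if that is intended. Prespecify the same 10% summary from the discharge-day assessment already scheduled in Section II as a sensitivity result. Use a paired analysis for both, in line with Section VII; the unpaired test in the XI (3) Analysis plan is named for clinical markers. Report the two results side by side, with the number of patients lacking a discharge score.
3. Reconcile the enrolment timing in Section II and in XI (3) Recruitment methods and Telehealth Intervention with the XI (3) Inclusion Criteria and XI (4)(c).

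The cost is a change of wording and one added contrast, with no new visit. The claim becomes less favourable, and some discharge scores will be missing; with 36 patients instead of 45, the 4-35% range becomes 5-36%. The discharge contrast leaves out any in-hospital device effect and may not cover quality of life. It is also still uncontrolled, with residual recovery in it, and a true fall of exactly 10% would miss the threshold about half the time. It should therefore limit the claim, not serve as a pass-fail rule or as evidence of efficacy.
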